8.2.2. Adverse Event Assessment and Reporting

All serious and non-SAEs will be recorded in the study's clinical database:

- AEs – from the day of first exposure to SL-901 through 30 days after the last dose of SL-901.
- SAEs – from the day of informed consent signature by the patient through 30 days after the last dose of SL-901.

This includes AEs that patients report spontaneously, those observed by the Investigator, and those elicited by the Investigator during scheduled study center visits.

All AEs entered into the clinical database are to contain the following details regarding the AE: diagnosis/AE term (in case diagnosis is unknown), start/stop date, intensity, relationship to study drug, action taken with study drug due to the event, whether intervention was required, outcome, and whether the event is classified as serious. The Investigator must continue to follow all SAEs and non-serious AEs until resolution, or until the Investigator assesses them as chronic or stable.

Each AE is to be assessed by the Investigator for the following categories.

Serious/Non-Serious

AEs that meet the criteria specified in [Section 8.2.1](#) are to be considered serious.

Relationship to Study Drug

The relationship of each AE to study drug is to be assessed by the Investigator according to the following criteria:

- **Related:** A temporal relationship exists between the event onset and administration of SL-901. It cannot be readily explained by the patient's clinical state, intercurrent illness, or concomitant therapies. In case of cessation or reduction of the dose, the event abates or resolves and reappears upon rechallenge. This includes events that are considered possibly, probably, or definitely related to SL-901.
- **Not Related:** Evidence exists that the AE has an etiology other than the study drug (e.g., pre-existing condition, underlying disease, intercurrent illness, or concomitant medication). This includes events that are considered probably not or not related to SL-901. It should be emphasized that ineffective study drug treatment should not be considered as causally related in the context of AE reporting (in other words, disease progression is not considered an AE; however some sequelae of disease progression may be reported as AEs and should generally be reported as AEs not related to investigational therapy).

An Investigator who is qualified in medicine must make the determination of relationship to the investigational product for each AE. The Investigator should decide whether, in his or her medical judgment, there is a reasonable possibility that the event may have been caused by the investigational product. The following factors for study drug relationship should be referenced when making a determination of "related" or "not related."

- **The temporal sequence from study drug administration:** The event should occur after the study drug is given. The length of time from study drug exposure to event should be evaluated in the clinical context of the event.
- **Underlying, concomitant, intercurrent diseases:** Each report should be evaluated in the context of the natural history and course of the disease being treated and any other disease the patient may have.
- **Concomitant medication:** The other medications the patient is taking or the treatment the patient receives should be examined to determine whether any of them might be recognized to cause the event in question.
- **Known response pattern for this class of study drug:** Clinical and/or preclinical data may indicate whether a particular response is likely to be a class effect.
- **Exposure to physical and/or mental stresses:** The exposure to stress might induce adverse changes in the recipient and provide a logical and better explanation for the event.

- The pharmacology and PK of the study drug: the known pharmacologic properties (absorption, distribution, metabolism, and excretion) of the study drug should be considered.

Intensity

The intensity of each AE is to be assessed by the Investigator according to the NCI CTCAE Version 5.0 (available at: https://ctep.cancer.gov/protocoldevelopment/electronic_applications/docs/CTCAE_v5_Quick_Reference_5x7.pdf). If the AE is not included in the NCI CTCAE, then the Investigator is to determine the intensity of the AE according to the following criteria:

Mild (Grade 1): AE that disappears or is easily tolerated on continuation of study drug.

Moderate (Grade 2): AE that disappears or is easily tolerated on continuation of study drug.

Severe (Grade 3): AE sufficiently discomforting to cause interference with usual work activities.

Life-Threatening (Grade 4): AE that is *potentially* life-threatening.

Death (Grade 5): Results in the patient's death.

A severe event is not necessarily a serious event. For example, a headache may be severe (interferes significantly with patient's usual function) but would not be classified as serious unless it met one of the criteria for serious events as previously defined.

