6.5. Rationale for the Dose(s) Selected

6.6. Dose Interruptions and Reductions

For patients that develop a clinically significant AE or unacceptable toxicity during treatment, dosing should be interrupted.

- If the toxicity resolves to the baseline level or Grade 1 within 7 days, then dosing should resume at the same dose level (during C2 and beyond, dose reduction may also be considered in consultation with the Sponsor).
- If the toxicity resolves to the baseline level or Grade 1 within 8 to 14 days, then dosing in C2 and beyond may be resumed at a reduced dose after consultation with the Sponsor.
- If the toxicity fails to resolve to baseline or Grade 1 within 14 days, then the patient should be discontinued from treatment permanently.

Specific management of unusual non-autoimmune and non-infectious toxicities known to be associated with PI3K inhibitors are summarized in [Table 6 \(Greenwell 2017\)](#).

Table 6: Management of Unusual Non-Autoimmune and Non-Infectious Toxicities

	Hypertension	Hyperglycemia	Confusion	Anxiety/ depression	Rash
Observe	BP \geq 140/90 mmHg	FG ULN-160 mg/dL	Mild disorientation	Mild symptoms	\leq 30% BSA
Hold Drug	BP \geq 200/110 mmHg	FG $>$ 160 mg/dL or NFG \geq 200 mg/dL	Limit ADL	Limit ADL	$>$ 30% BSA

Abbreviations: ADL = activities of daily living, BP = blood pressure, BSA = body surface area, FG = fasting glucose, NFG = non fasting glucose, ULN = upper limit of normal

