8.2. Adverse Events and Serious Adverse Events

8.2.1. Definitions

Adverse Event (AE)

An AE is any untoward medical occurrence in a study patient who is administered a medicinal product (study drug), regardless whether or not considered drug-related. An AE can therefore be any unfavorable and unintended sign including abnormal laboratory/examination findings, symptoms, or disease(s) temporally associated with the use of study drug, whether or not related to study drug. An AE can arise from any use of the drug (e.g., off-label use, use in combination with another drug) and from any route of administration, formulation, or dose, including an overdose.

Serious Adverse Event (SAE)

An AE is considered serious (i.e., an SAE) if, in the view of either the Investigator or Sponsor, it meets any of the following criteria:

- Results in death.
- Is life-threatening. Life-threatening means that the patient was at immediate risk of death from the reaction as it occurred (i.e., it does not include a reaction which hypothetically might have caused death had it occurred in a more severe form).
- Requires in-patient hospitalization or prolongation of existing hospitalization. Hospitalization admissions and/or surgical operations scheduled to occur during the study period, but planned before study entry are not considered adverse events if the illness or disease existed before the patient was enrolled in the study, provided that it did not deteriorate in an unexpected manner during the study (e.g., surgery performed earlier than planned).
- Results in persistent or significant disability/incapacity or substantial disruption of the ability to conduct normal life functions.
- Results in a congenital anomaly/birth defect.

Important Medical Event (IME)

An important medical event (IME) that may not result in death, be life-threatening, or require hospitalization may be considered serious when, based upon appropriate medical judgment, it may jeopardize the patient or subject and may require medical or surgical intervention to prevent one of the outcomes listed in the definitions for SAEs.

Note: The onset date of an SAE is defined as the date on which the event initially met serious criteria (e.g., the date of admission to a hospital). The end date is the date on which the event no longer met serious criteria (e.g., the date the patient was discharged from a hospital).

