7.2.2. Key definitions

Baseline

Baseline is defined as the last non-missing assessment prior to the date and time of the first SL-901 dose.

Change from Baseline

Change from Baseline (absolute value) = post-baseline value – baseline value.

Adverse Events (AEs)

An AE is any untoward medical occurrence in a study patient who is administered a medicinal product (study drug), regardless whether or not considered drug-related. An AE can therefore be any unfavorable and unintended sign including abnormal laboratory/examination findings, symptoms, or disease(s) temporally associated with the use of study drug, whether or not related to study drug. An AE can arise from any use of the drug (e.g., off-label use, use in combination with another drug) and from any route of administration, formulation, or dose, including an overdose.

Treatment-Emergent Adverse Events (TEAEs)

If an Adverse Event occurs for the first time or if it worsens in terms of grade, seriousness or severity on or after the first on or after the date and time of the first dose of SL-901 and up to 30 days after the last dose of SL-901, it will be classified as TEAE, otherwise it will be classified as non-TEAE. Where an AE date is partial or missing, and it is unclear whether the AE is treatment-emergent, the AE will be assumed to be treatment-emergent.

Adverse Drug Reactions (ADRs)

Untoward and unintended responses to an Investigational Medicinal Product (IMP) related to any dose administered. The definition also covers medication errors and uses outside what is foreseen in the protocol, including misuse and abuse of the product. The definition implies a 'reasonable possibility of a causal relationship between the event and the IMP. This means that there are facts (evidence) or arguments to suggest a causal relationship.

All AEs (including SAEs) are to be accurately recorded on the AE page of the patient's electronic case report form (eCRF). Each event will be graded for severity using the classifications of NCI CTCAE (see section 6.3.3).

- **Grade 1 / Mild** - AE that disappears or is easily tolerated on continuation of study drug;
- **Grade 2 / Moderate** – AE that disappears or is easily tolerated on continuation of study drug;
- **Grade 3 / Severe** - AE sufficiently discomforting to cause interference with usual work activities;
- **Grade 4 / Life-threatening** - AE that is potentially life-threatening.
- **Grade 5 / Fatal** - Results in the patient's death.

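### Grade 1 and Grade 2 share one definition in the fallback severity scale for adverse events outside NCI CTCAE, so that boundary cannot be determined for those events

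*Protocol*

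**What the plan says.** Protocol 8.2.2, under Intensity, has the investigator grade each adverse event (AE) by NCI CTCAE v5.0. A second scale, with five levels, is a fallback only, introduced by the words "If the AE is not included in the NCI CTCAE, then the Investigator is to determine the intensity of the AE according to the following". The first level reads "Mild (Grade 1): AE that disappears or is easily tolerated on continuation of study drug". The second reads "Moderate (Grade 2): AE that disappears or is easily tolerated on continuation of study drug".

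SAP 7.2.2 states "Each event will be graded for severity using the classifications of NCI CTCAE (see section 6.3.3" and directly beneath sets out the same five levels, again with one text for Grades 1 and 2. It does not repeat the protocol's restriction to events that CTCAE does not include. SAP 6.3.3, to which it refers, names CTCAE v5.0 and no other scale.

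**The concern.** A severity scale must let two investigators who see the same event reach the same grade. Here the lowest two levels differ only in their labels, so a site that records Grade 1 and a site that records Grade 2 have both followed the text. The boundary is used: Protocol 6.6 makes return to dosing or permanent discontinuation depend on it, the SAP uses change of grade to decide whether an event is treatment-emergent (a TEAE), and the safety tables report maximum grade. Safety is a primary objective of this study.

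**Working it through.** No arithmetic figure in the plan is at issue. The check compares the definitions and then traces each threshold to the scale that governs it.

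**Step 1: compare the definitions.** The two documents give the same content at every level.

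| Grade | Definition in Protocol 8.2.2 and SAP 7.2.2 | Distinct from the grade below? |
|---|---|---|
| 1 | tolerability wording | not applicable |
| 2 | the same tolerability wording | no |
| 3 | "Severe (Grade 3): AE sufficiently discomforting to cause interference with usual work activities" | yes |
| 4 | potential threat to life | yes |
| 5 | death | yes |

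Five grades have 5 − 1 = 4 distinct definitions, and 4 − 1 = 3 of the four adjacent boundaries can be told apart. Only the 1/2 boundary fails. In addition, an event that is not easily tolerated but leaves usual work unaffected fits no definition.

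**Step 2: thresholds that the duplicate reaches.**

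- *Restart and discontinuation (Protocol 6.6).* This section names no scale, so 8.2.2 supplies it. The condition for permanent discontinuation begins "If the toxicity fails to resolve to baseline or Grade 1 within 14 days", and the two restart rules use the same target. Take a toxicity outside CTCAE that led to an interruption, has improved until it is easily tolerated, and is still above baseline at 14 days. The baseline route is not met. On the grade route, Grade 1 means resolved and Grade 2 means not resolved, and the text fits both.
- *Treatment emergence (SAP 7.2.2).* An event counts if it first occurs, or worsens in grade, seriousness or severity, after the first dose. On this scale a change from Grade 1 to Grade 2 cannot be identified. First occurrence, a change to Grade 3 or above, and worsening in seriousness can.
- *Maximum-grade tables (SAP 11.5.2; Tables 14.3.1.1.4, 14.3.1.2.2, 14.3.1.3.2 and 14.3.1.4.2).* Each patient is counted once per system organ class or preferred term, at the worst grade. Let k be the number of patients in a given row whose worst grade rests on a Grade 1 or 2 event outside CTCAE. The Grade 1 and Grade 2 counts can each move by up to k, in opposite directions. Their sum and all counts at Grade 3 or above do not change. The documents do not give k, and it may be zero.

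**Step 3: thresholds that the duplicate does not reach.**

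- *Exclusion criterion 5 (Protocol 5.2)* is set at Grade 2 or higher, but it names CTCAE v5.0 as its scale and concerns toxicity from previous therapy. The fallback scale is for AEs, and "An AE is any untoward medical occurrence in a study patient who is administered a medicinal product (study drug"). Non-serious events are recorded only from dosing: "AEs – from the day of first exposure to SL-901 through 30 days after the last dose of SL-901".
- *Dose-limiting toxicities (Protocol 6.4.2)* are assessed by CTCAE v5.0, and the graded criteria are set at Grade 3 or 4. Two side conditions use the Grade 1 line: recovery of symptom-free Grade 3 laboratory abnormalities, and bleeding that accompanies Grade 3 thrombocytopenia. Section 6.4.2 names CTCAE for both, and Protocol 9.3.4.1 leaves laboratory results without a CTCAE term ungraded.

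**The case against.** The strongest reply is that this is a copying slip in a scale seldom used. CTCAE v5.0 is the operative scale in Protocol 8.2.2 and SAP 6.3.3, and the labels mild and moderate still carry their ordinary meaning. Protocol 6.6 applies only after a clinically significant AE or unacceptable toxicity, so an event that was easily tolerated throughout would not normally enter it, and return to baseline needs no grade. On treatment emergence, Protocol 8.1.4 and 8.3 send clinically significant pre-dose findings to medical history and report later worsening as an AE, which is then emergent by its onset date. The study also stopped early and Part 1b was not started (SAP 4), so new protocol wording would guide little future grading.

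Much of this stands, and it narrows the point. A reader might infer from SAP 7.2.2 that the ambiguity touches every Grade 1 or 2 AE, because the scope limit is missing there. The documents do not support that: investigators assign grades under Protocol 8.2.2, and the SAP tabulates recorded grades. The omission is a transcription flaw and does not create a second grading system.

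Three things remain. Labels give an order but no criterion. The case under Protocol 6.6 is a corner case, but the two readings lead to opposite outcomes. The treatment-emergence route is narrow but not empty, because SAP 11.5.2 sends only events before the start of screening to medical history, so an AE recorded during screening could later worsen.

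**Conclusion.** The defect is real: Grades 1 and 2 cannot be told apart in either document, and no other section separates them. It is confined to AEs outside CTCAE v5.0 and to one of four boundaries. Within that scope, three uses are arbitrary: the Grade 1 route of the Protocol 6.6 test when baseline has not been regained, Grade 1 to 2 worsening in the SAP's TEAE definition, and the split between the Grade 1 and Grade 2 rows of the maximum-grade tables.

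A reader might also infer that eligibility is compromised, or that the grade thresholds as a whole cannot be applied. Neither follows. Exclusion 5 has its own named scale. The baseline route, the anchors from Grade 3 upward and the seriousness criterion all remain usable.

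The conclusion assumes that Protocol 6.6 takes its grades from 8.2.2, since it names no scale itself. The size of the effect is unknown, because the number of events outside CTCAE is not given. The documents do not show what Grade 2 wording was intended.

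**What to change.** 1. The sponsor should reconcile the duplicate by giving Grade 2 a definition that differs from Grade 1 and is consistent with the existing Grade 3 wording, in identical text in Protocol 8.2.2 and SAP 7.2.2. Because this boundary bears on restart and discontinuation, the wording is for the sponsor to supply, and none is proposed here.
2. Restore in SAP 7.2.2 the limit that this scale applies only to AEs not included in CTCAE v5.0.
3. Add to the agenda of the data review meeting (SAP 7.4.2) a review of recorded Grade 1 and Grade 2 gradings of AEs outside CTCAE, before database lock. This would also show how many events are involved.

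The cost is about a sentence in each document and a few site queries. With the study stopped early, most of the practical gain lies in the second and third steps.

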8.2.3. Reporting Serious Adverse Events

The Investigator must report all SAEs within 24 hours of discovery via e-mail to the Sponsor's Safety Vendor at the following e-mail:

[contact]

The completed SAE report is to be sent within 24 hours of discovering the event. The initial report should include at least the following information:

- Patient's study identification number
- Date, description and time (if available) of the event
- Criterion for seriousness
- Preliminary assignment of relationship to study drug

The Safety Vendor will confirm receipt of the report. The Sponsor will review the report and determine if any follow-up queries are needed for the study site. The Investigator will be contacted for follow-up information regarding the SAE, as appropriate. Follow-up reports should be sent in a timely fashion as information becomes available.

SAEs that are considered at least possibly related to the investigational product and unexpected (i.e., Suspected Unexpected Serious Adverse Reactions [SUSARs]), will be

reported to the applicable regulatory authorities and IRB/EC by the Sponsor or Sponsor's designee as required by applicable local regulations. Per regulation, any fatal or life-threatening SUSAR will be reported to the regulatory authorities and IRB/EC within 7 calendar days, and additional information within an additional 8 calendar days. The Sponsor or Sponsor's designee is required to submit any other SUSAR to the regulatory authorities and IRBs/ECs within 15 calendar days of notification. The Sponsor or its designee is also responsible for notifying the investigational sites of all expedited SAEs. The Investigator must keep copies of all expedited SAE information including correspondence with the Sponsor on file.

8.2.4. Special Cases: Overdose and Pregnancy

Overdose is defined as an occurrence in which more drug is administered than the intended amount. Signs and symptoms considered to be a result of an overdose should be reported as AEs. Overdoses will not be considered SAEs unless the outcome of the overdose meets seriousness criteria (see [Section 8.2.1](#)).

Pregnancies or pregnancies of partners by study patients occurring while the patient is receiving SL-901 or within 30 days after the patient's last dose of SL-901 will not be considered serious, but are to be reported using the same procedures as for SAEs described in [Section 8.2.1](#) as IMEs.

8.2.5. Protocol Deviations Due to an Emergency or Adverse Event

Generally, deviations from the protocol require pre-approval by the Sponsor on a case-by-case basis. In medical emergency situations, the Investigator or other physician in attendance may exercise their medical judgment without prior approval but will need to subsequently report the deviation to the Sponsor.

8.3. Laboratory Assessments

Laboratory abnormalities that are considered by the Investigator to be clinically significant for a particular patient during Screening and before the first study drug dose are to be reported as part of the patient's medical history. After the first study drug dose, any clinically significant (as determined by the Investigator) worsening in laboratory assessments or other clinical findings should be considered an AE.

Blood samples for hematology and clinical chemistries are to be collected at the time points designated in [Table 1](#) and [Table 2](#).

The laboratory parameters that will be measured during the study are summarized in [Table 7](#).

Table 7: Clinical Laboratory Parameters to be Measured During the Study

Hematology	Hematocrit Hemoglobin Platelet count White blood cell count with differential
Chemistry	Alanine aminotransferase (ALT) Albumin Alkaline phosphatase Aspartate aminotransferase (AST) Bilirubin Bicarbonate Blood urea nitrogen Calcium Chloride Creatinine Glucose Lactate dehydrogenase Magnesium Phosphate Potassium Sodium Total protein Uric acid
Coagulation	Prothrombin time or international normalized ratio

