6.4.2. Dose-Limiting Toxicities

Patients are to receive at least 75% of the planned SL-901 doses in C1 and complete study assessments through C2D1 to be eligible for DLT evaluation, unless discontinuing due to DLT. Patients who receive <75% of the planned SL-901 doses in C1 and/or discontinue before completing study assessments through C2D1 for reasons other than DLT are to be replaced.

Toxicities are to be assessed by the Investigator according the NCI CTCAE, v5.0 (available at:

https://ctep.cancer.gov/protocoldevelopment/electronic_applications/docs/CTCAE_v5_Quick_Reference_5x7.pdf.

A DLT occurring during the Run-in PK period or in C1 is defined as any of the following AEs for which there is a reasonable possibility that SL-901 caused the event. (Note that while causality of an AE is to be determined by the Investigator, the Sponsor's assessment of causality can be used to override an Investigator's designation of 'unrelated'; however, the Sponsor's assessment cannot be used to reverse an Investigator's designation of 'related' for the purpose of DLT determination.

- Any \geq Grade 3 non-hematologic AEs, with the exceptions of:
 - Grade 3 nausea, vomiting, diarrhea, constipation, fever, fatigue, or skin rash that resolves to Grade <3 within 72 hours.
 - Grade 3 laboratory abnormalities that are not associated with symptoms and resolve to Grade 1 or baseline by C1D28 (unless otherwise specified).
- Grade 4 thrombocytopenia or Grade 3 thrombocytopenia with $>$ Grade 1 bleeding or requirement for platelet transfusion.
- Grade 4 neutropenia lasting >5 days.
- Febrile neutropenia (ANC $<1\times10^9/L$ with fever $\geq38.5^{\circ}\text{C}$) of any duration.
- Persistent anemia (i.e., lasting >96 hours despite >2 red blood cell [RBC] transfusions).
- \geq Grade 3 transaminase (AST/ ALT) elevation.
- Any toxicity resulting in >7 held/skipped doses.
- Any other significant toxicity considered by the Investigator or the Sponsor to be dose-limiting (e.g., any toxicity considered at least possibly related to SL-901 that results in patient withdrawal during C1).

In situations in which DLTs have occurred that would prevent further dose-escalation and are severe but not life-threatening (i.e., persistent Grade 3 fever, malaise), re-evaluation of specific dose cohorts may be considered with co-administration of appropriate supportive care agents (e.g., corticosteroids, anti-depressants) concomitant with SL-901 therapy.

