11.5.7. Safety laboratory tests

Laboratory parameters, including haematology, chemistry and coagulation, will be summarized using descriptive statistics both in terms of absolute values and change from baseline at each visit.

Laboratory values will be reported in SI units and will be compared to the relevant reference range in SI units and categorized as follows:

- Low: < lower limit of the reference range
- Normal: \geq lower limit of the reference range and \leq upper limit of the reference range
- High: > upper limit of the reference range.

Shift tables of laboratory parameters from baseline to the worst post-baseline low/normal/high categorization will be performed; in the shift tables, percentages will be calculated based on the number of subjects that have valid data for both baseline and at least 1 post-baseline assessment.

For analysis purposes, values preceded by a “<” or “>” sign will be considered equal to the lower or upper limit of quantification, respectively.

All laboratory parameters, including low/normal/high categorization, will be listed.

Results from unscheduled visits will not be included in the summary tables but will only be listed.

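### Protocol 8.2.1, 8.3 and 6.4.2 are unreconciled, so a laboratory value that meets a listed DLT criterion can be left out of the formal DLT count

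*Protocol*

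**What the plan says.** Three protocol sections bear on whether a laboratory result becomes a DLT.

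- **Section 6.4.2 (DLTs).** A DLT in the run-in or Cycle 1 "is defined as any of the following AEs for which there is a reasonable possibility that SL-901 caused the event". The list includes laboratory events fixed by grade, or by grade and duration: at or above the stated grade, "Grade 3 transaminase (AST/ ALT) elevation"; "Grade 4 neutropenia lasting >5 days"; and Grade 4 thrombocytopenia. Among non-hematologic events it exempts "Grade 3 laboratory abnormalities that are not associated with symptoms and resolve to Grade 1 or baseline by C1D28 (unless otherwise specified"). None of these entries asks whether the investigator thinks the value matters clinically. SAP 5.1 repeats the list.
- **Section 8.3 (laboratory assessments).** After the first dose, "any clinically significant (as determined by the Investigator) worsening in laboratory assessments or other clinical findings should be considered an AE".
- **Section 8.2.1 (definitions).** An AE can be "any unfavorable and unintended sign including abnormal laboratory/examination findings, symptoms, or disease(s) temporally associated with the use of study drug". There is no clinical-significance condition. SAP 7.2.2 repeats this definition, but its causality categories mention laboratory abnormalities only where they have been assessed as clinically significant.

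On analysis, Protocol 9.3.4.1 promises CTCAE grading of laboratory results. SAP 11.5.7 instead says that values "will be compared to the relevant reference range in SI units and categorized as follows": low, normal or high. It keeps unscheduled results out of the summary tables. SAP 3.1, which lists changes from the protocol, does not mention the loss of grading. SAP 11.5.2 summarizes DLTs as a category of TEAEs.

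**The concern.** The DLT criteria are objective, but entry to the AE record may not be. If a site treats 8.3 as the test for a laboratory AE, an asymptomatic value that meets a 6.4.2 criterion and is marked not clinically significant never becomes an AE. It then cannot be a DLT under 6.4.2, and cannot reach Table 14.3.1.1.2 or Listing 16.2.7.3. If the patient took enough doses and completed assessments through C2D1, the patient stays in the DLT population of SAP 7.3 as someone without a DLT.

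A 3+3 rule turns on single events, so one uncounted patient can change a decision. Finding the MTD is a primary objective and identifying DLTs is part of the primary endpoints. Laboratory toxicity is foreseen for this drug class: Protocol Table 6 includes hyperglycemia.

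**Working it through.** **Step 1. Set the texts side by side.**

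| Question | 6.4.2 | 8.3 | 8.2.1 |
|---|---|---|---|
| Must it be an AE to count as a DLT? | Yes | not addressed | not addressed |
| Is clinical significance needed for a laboratory value? | Not mentioned | Attached to the AE rule | Not mentioned |
| Can an asymptomatic value qualify? | Yes, if the listed exception is not met | Depends on the investigator | Yes |

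No section says which rule prevails, or that a value meeting a listed criterion is an AE whatever the clinical-significance judgement. The Sponsor's corrective power in 6.4.2 is limited to cause: the Sponsor's "assessment of causality can be used to override an Investigator" designation of unrelated. It does not reach clinical significance or AE status.

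**Step 2. Apply the escalation rule in Protocol 6.4.1 with one laboratory DLT uncounted.**

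| True count | Recorded count | Action on true count | Action on recorded count |
|---|---|---|---|
| 1 of 3 | 0 of 3 | add up to 3 patients | escalate without expansion |
| 2 of 3 | 1 of 3 | stop, next lower dose is the MTD | add up to 3 patients |
| 2 of 6 | 1 of 6 | stop, next lower dose is the MTD | escalate |

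The last row also bears on the MTD definition in SAP 5.1, which allows at most 1 DLT in 6. This step needs no assumption about rates. The omission only removes events, so it works in one direction.

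**Step 3. Illustrate the effect on the chance of escalating.** The plan gives no operating characteristics to reproduce. Its only related figure, the 33% marginal DLT rate in Protocol 9.1, is 1/3. For a recorded DLT rate q, with independent patients, a full second group of 3 and the rule followed mechanically:

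P(escalate) = (1 − q)³ + 3q(1 − q)² × (1 − q)³

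Take a true rate of 0.33, and assume one third of DLTs are laboratory-only.

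- None uncounted: q = 0.33. P = 0.301 + 0.134 = 0.434.
- Half of the laboratory-only DLTs uncounted: q = 0.33 × (1 − 1/3 × 1/2) = 0.275. P = 0.381 + 0.165 = 0.546.
- All of them uncounted: q = 0.33 × (1 − 1/3) = 0.22. P = 0.475 + 0.191 = 0.665 (66.5%).

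More generally, with true rate p and a share m of all DLTs uncounted, q = p(1 − m):

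| p | m = 0 | m = 0.10 | m = 0.25 | m = 0.50 |
|---|---|---|---|---|
| 0.25 | 0.600 | 0.654 | 0.736 | 0.862 |
| 1/3 | 0.428 | 0.494 | 0.600 | 0.780 |
| 0.50 | 0.172 | 0.234 | 0.351 | 0.600 |

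The true rate, the laboratory-only share and the uncounted share are all assumptions. The earlier clinical experience in Protocol 2.1.2.2 reports no DLTs up to 40 mg/day, so it informs neither share.

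**The case against.** The case for leaving the text alone is substantial.

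- Section 8.3 does not contain the word only. Literally, it says that clinically significant worsening is enough to make an AE, not that it is necessary. Section 8.2.1 is the broader definition, and 8.2.2 requires all AEs to be recorded.
- Section 6.4.2 calls the graded values AEs. Its exception for symptom-free Grade 3 abnormalities would have little purpose if such values could not be AEs. As the specific DLT rule, it can be read as controlling.
- Protocol 6.4.3 has a committee look at safety and other data under a charter not available here. SAP 7.4.1 records weekly cohort meetings. Either the investigator or the Sponsor may call another toxicity dose-limiting.
- SAP 11.5.7 lists every laboratory parameter, so a qualifying value would be visible to someone who looked.

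All of this stands, and it limits the point. A reader might infer that 8.3 flatly bars such values from the AE record, or that the planned outputs would conceal them. The documents support neither inference: the first is one reading among two, and the listings show the values. But none of these routes obliges anyone to count the value. The committee's duty is general, the power to name another toxicity is discretionary, and the listings are not planned to carry grades. The SAP's causality wording also leans toward the narrower reading.

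**Conclusion.** The point holds as an unreconciled conflict between 8.2.1, 8.3 and 6.4.2. On one natural reading of 8.3, a value that meets a listed DLT criterion can be missing from the formal count, and any such error lowers the count. That follows from the text and the escalation rule alone.

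Its size is unknown. The rise from 43% to 55% or 66.5% shows how sensitive a 3+3 design is to undercounting under assumed shares. It does not measure the effect of this wording. The 66.5% case needs every laboratory-only DLT to be dismissed, including prolonged Grade 4 neutropenia.

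A reader might also infer that doses in this trial were escalated wrongly. Nothing in the documents shows that a DLT was missed. SAP section 4 says that the study was stopped early and Part 1b was not started, so what can still be protected is the accuracy of the reported DLTs and of any MTD statement.

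**What to change.** **Protocol.** Reconcile 8.2.1, 8.3 and 6.4.2 with one sentence: any laboratory value in the run-in or Cycle 1 that meets an existing 6.4.2 criterion is recorded as an AE and assessed for DLT, including cause, whatever the clinical-significance judgement. No threshold changes.

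**SAP.** In 11.5.7, restore the CTCAE laboratory grading of Protocol 9.3.4.1. Apply it to all values in the DLT window, including unscheduled ones. Reconcile the graded values with Listing 16.2.7.3 and Table 14.3.1.1.2 before database lock, and resolve each mismatch with the site and Sponsor.

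**Cost.** One sentence in the protocol, a short SAP addition, one reconciliation program and a few more asymptomatic laboratory AEs. With the study stopped, the SAP step is the one that can still act: it can correct the reported DLTs and any MTD statement, but it cannot alter escalation decisions already taken.
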